## 6.2. Subject Selection

Subject study selection is governed by the inclusion/exclusion criteria defined in the CIP. Subjects that meet all inclusion criteria and no exclusion criteria and who have signed an informed consent form will be eligible for enrollment.

## 6.3. Study Objectives

The primary study objective is to determine if the hemostatic efficacy of MIR-treated plasma stored Trima Accel® Aph PLTs (MIRASOL) is non-inferior to Conventional plasma stored Aph PLTs (CONTROL) in subjects with hypoproliferative thrombocytopenia requiring PLT transfusions.

The secondary study objectives include comparing other efficacy and safety endpoints between the MIRASOL and CONTROL groups.

Unless otherwise specified, comparisons of each endpoint will be presented as (MIRASOL vs CONTROL). The primary analyses will be based on the observed data in the mITT set. The secondary and exploratory endpoints are summarized below. An in-depth discussion of the analysis of these

endpoints is provided in Sections 8.1 to 8.3, respectively. The safety endpoints are also summarized below and are discussed in detail in Section 8.4

### 6.3.1. Primary Endpoint

The primary study objective will be assessed through examination of the Primary Efficacy Endpoint where clinical effectiveness will be measured by comparing the days of grade 2 or higher bleeding over the treatment period between the MIRASOL and CONTROL groups. Specifically, this study will investigate whether MIR-treated Aph PLTs (MIRASOL) are non-inferior to conventional PLTs (CONTROL) by testing the null hypothesis that the MIRASOL arm is inferior to the CONTROL arm. The null hypothesis will be tested using a one-sided alpha level of 0.025. If NI is established, superiority of MIR-treated Aph PLTs vs Conventional PLTs will be tested using a one-sided alpha level of 0.025 by employing a closed “gate keeper” multiple testing strategy. An in-depth discussion of the analysis of the primary efficacy endpoint is provided in Section 8.1 of this document.

### 6.3.2. Secondary, Exploratory, and Safety Endpoints

The Key Secondary Endpoint is human leukocyte antigen (HLA) alloimmunization defined as a binary response indicating the occurrence of alloimmunization.

#### Additional Secondary Endpoints:

1. Occurrence of World Health Organization (WHO)  $\geq$  grade 2 bleeding
2. Time to first day of WHO  $\geq$  grade 2 bleeding
3. Occurrence of WHO  $\geq$  grade 3 bleeding
4. Occurrence of PLT refractoriness defined as 2 sequential transfusion episodes, each with corrected count increments (CCIs)  $<$  5000 measured 1-hour post-transfusion
5. Occurrence of PLT refractoriness as defined above and with a positive antibody test within 14 days before or after the onset of PLT refractoriness
6. Number of PLT transfusion episodes per subject, i.e., frequency of transfusion
7. Days of PLT support; the number of days from the first to the last PLT transfusion
8. PLT utilization (average number of PLTs transfused)
9. CCIs at 1 hour and  $\geq$  18 but  $<$  30 hours post-PLT transfusion(s)
10. Total number of red blood cells (RBC) transfusions (number of units)/subject

#### Exploratory Endpoints:

1. Total number of units of PLTs transfused/day of PLT support
2. Total number of PLTs (PLT dose) transfused/body surface area (BSA)/day of PLT support
3. Interval between PLT transfusion episodes (days)
4. PLT refractoriness defined as 2 sequential transfusion episodes, each with CCIs  $<$  7500 measured 1-hour post-transfusion

#### Safety Endpoints

1. Treatment-emergent adverse events (TEAEs)
2. Transfusion-related adverse events (AEs)
3. Serious adverse events (SAEs)
4. Unanticipated adverse device effects (UADEs)
5. Pulmonary events
  - a. Subjects on assisted ventilation
6. All-cause mortality
7. Death due to bleeding as the primary or contributory cause of mortality

### 6.3.3. Sample Size

A total of approximately 558 mITT subjects will be randomized in a 1:1 fashion to MIRASOL:CONTROL. This sample size estimate accounts for 10% of subjects who are randomized but will never receive an on-study transfusion and thus, will not be included in the mITT analysis set and, therefore, the primary analysis. A total of 558 mITT subjects in MIRASOL versus CONTROL will provide approximately 85% power for establishing non-inferiority at the 1-tailed 0.025 level of significance (using a 2-sided 95% CI) accommodating a 10% relative increase in the mean rate of WHO grade 2 or higher bleeding (i.e.  $\mu_T / \mu_C = 1.1$ ).

## 7. Database Description

A comprehensive database description can be found by referencing the Terumo BCT CTS-5030 Data Management Plan (DMP). Two data sources will be used for study analysis, a clinical study database and a central laboratory database.

The clinical study database will be populated by an Electronic Data Capture (EDC) system which is developed and hosted by IBM Clinical Development using the eClinicalOS™ software platform. Data integrity will be maintained by conducting both internal and external data checks as described in the DMP. The clinical database will be used to create tables, figures, and listings (TFLs) for both the interim and final analyses.

Additionally, HLA antibody results are maintained exclusively by BSRI. Blood System Research Institute will be responsible for analyzing all data related to HLA and alloimmunization. Details of this analysis are provided in Appendix II of this SAP.

### 7.1. Creating Analysis Data Sets

To enable analysis of study data, it will be necessary to derive analysis datasets from raw variables in the clinical study database. All data and processing will be completed using SAS® version 9.4 or higher.

### 7.2. Validation of Data and Analysis Programs

All programs created by CPC to create analysis datasets, produce TFLs, or to perform statistical analysis will be generated according to CPC SOP-BDM-C-002: Developing Data Analysis Programs. Additionally, all datasets, output, and statistical analysis produced by CPC will be validated according to CPC SOP-BDM-C-003: Statistical Validation.

### 7.3. Archiving Data and SAS® Files

Following database lock, the SAS® programs used to analyze data for the final CIR will be executed and archived according to CPC SOP-BDM-C-002: Developing Data Analysis Programs.

The final analyses will be conducted on locked clinical study data using SAS® version 9.4 or higher. Unless specified otherwise, all analyses related to the primary, secondary and exploratory endpoints will involve the direct comparison of the MIRASOL and CONTROL arms.

To ensure integrity and internal consistency of all data points used for the IA, the biostatistics group will define data elements needed for the IA and work with the clinical data manager to determine which electronic case report forms (eCRFs) need to be cleaned. The identified data elements and timing of the IA will then be communicated to the appropriate study team members to facilitate timely collection and cleaning in preparation for the IA. All efforts will be made to fully monitor and resolve critical queries on the IA data elements. At the time of the data cut for the IA, all data in the clinical database will be used. As this is an ongoing study, outstanding queries may remain, and/or some data entered at the time of the data cut may not have been monitored.

## 7.4. Analysis Conventions

The following general conventions will be used for conducting all statistical analyses, where, departures from these conventions are defined in a more precise manner in specific sections of this SAP. In these instances, rules established in the specific sections take precedence over the general convention.

- Formal hypothesis testing will be performed on the primary outcome using a closed testing procedure with a first test of non-inferiority followed by a test of superiority if non-inferiority is demonstrated.
- Key secondary and secondary efficacy outcomes will be tested but viewed as supportive and exploratory.
- The distribution of continuous variables will be summarized using means, standard deviations (SD) and/or standard errors, medians, minimums (or 25th percentile), and maximums (or 75th percentile) and the number of subjects with non-missing data.
- Mean/median/quartiles are presented to one decimal more than the measured value. Minimum/Maximum are reported to the same number of decimals as the measured value. Standard deviation is presented to two decimals more than the measured value.
- Summary of discrete variables will consist of the number and percent of responses in each category. All percentages will be rounded to one decimal place. The count and percentage of responses will be presented in the form of “XX (XX.X%)”, where the percentage is in parentheses. If the count is “0” then the percentage may not be presented to draw attention to the non-zero count cells. If zero percentages are displayed these will be shown as “0.0%”. If the percentage is “100”, the decimal place may be dropped. In addition, the decimal place may also be dropped due to space constraints within a table where this does not impact the interpretation of results.
- All Medical History and AEs will be coded using Medical Dictionary for Regulatory Activities (MedDRA) Version 19.1.
- All medications will be coded using the World Health Organization Drug Dictionary Enhanced (WHO DDE) version dated 01Sep2016.
- Uncoded AE terms will be included with a System Organ Class (SOC) and Preferred Term (PT) of “Uncoded”.
- Leading zeros will be used for decimal values less than one. For example, “0.05” will be used rather than “.05.”
- All tables will clearly indicate the sample sizes contributing to the summary data in the column heading and labeled as “*Treatment* (N=)”. For example, if a table reports data for the Full Analysis Set (FAS) population, N would represent all subjects in the FAS. If a table reports data for the Safety Set (SS), N would represent all subjects in the SS. Within the table the small “n” will represent the number of subjects within the population of interest who have non-missing data or data otherwise available for the summary measures of interest (i.e. the denominator for a subset of the overall population being presented in the summary). If no data are available for a TFL, the output will be produced with “No data to display”. Footnotes which are data driven may be applied to the TFLs as needed. These changes will not necessarily be made to the mock TFLs.
- Percentages are calculated out of the header N unless otherwise footnoted.
- Duration of periods of time will be calculated in days as (stop date – start date + 1) in order to include both the starting day and final day of the periods of time. Conversions to weeks, months, or years will be calculated as days/7, days/30.4375, or days/365.25, respectively.
- In general, missing values will be handled as follows: for continuous variables at baseline, missing values will be excluded from calculation of summary statistics and the n of subjects reporting will be reported. For categorical values at baseline, the number and percent of subjects with missing values will be displayed. Handling of missing postbaseline values will depend on the analysis.

### **7.4.1. Dropouts and Missing Data**

Handling of subject dropouts and other forms of missing data with regard to the primary endpoint will be discussed in Section 8.1. Handling of subject dropouts and other forms of missing data with regard to key secondary endpoints is the responsibility of BSRI. No imputation of missing data will be applied to secondary, exploratory or safety endpoints unless otherwise specified.

### **7.4.2. Adjustments for Covariates**

Covariate adjustment will be utilized in both supporting and subgroup analysis of the primary endpoint and is discussed in Section 8.

### **7.4.3. Multi-center studies**

Data from each of the study sites will be pooled for summarization and analysis unless otherwise specified.

### **7.4.4. Multiplicity Issues**

As described in FDA's Guidance for Industry: Non-inferiority Clinical Trials, testing for superiority after successfully establishing non-inferiority is possible so long as Type I error control is maintained. For this study, a sequential testing strategy will be employed, whereby if the primary endpoint is positive in the sense that non-inferiority is concluded, a test for superiority will be performed for the primary endpoint with the same one-sided type I error rate.

No adjustments for multiple comparisons/testing will be performed for the key secondary, secondary or exploratory endpoints.

## **7.5. Analysis Populations**

The study analysis populations (sets) are defined in Sections 7.5.1 thru 7.5.4.

### **7.5.1. Full Analysis Set**

The FAS is defined as containing all randomized subjects, wherein subjects will be analyzed based on their assigned treatment group (MIRASOL or CONTROL) at the time of randomization.

### **7.5.2. Modified Intent-to-Treat Analysis Set**

The mITT analysis set is defined as containing all randomized subjects who undergo at least one (1) study transfusion post-randomization based on the treatment group to which they were randomized. Subjects will be analyzed according to the treatment group (MIRASOL or CONTROL) they were assigned at randomization.

### **7.5.3. Safety Set**

The SS is defined as containing all subjects who have been randomized and undergo at least one (1) PLT transfusion post-randomization, independent of the outcome or successful completion of the procedure. Subjects will be analyzed according to the majority treatment (transfusion type: MIRASOL or CONTROL) received. If there is a tie, i.e. no majority treatment exists, then the subject will be classified into the treatment group to which they were randomized.

### **7.5.4. Per Protocol Set**

The Per Protocol Set (PPS) is defined as containing all randomized subjects who undergo at least 75% of post-randomization PLT transfusions as per the protocol treatment allocation and have not experienced any major protocol deviations (as described in Section 7.12). For instance, if a subject is randomized to

the MIRASOL arm and has 4 transfusions, 3 of those transfusions must contain MIR-treated Aph PLTs if the subject is to be included in the PPS. Similarly, if the subject had 3 transfusions, all 3 transfusions must contain MIR-treated Aph PLTs if the subject is to be included in the PPS. Subjects eligible for the PPS will be analyzed according to the treatment group to which they were assigned at randomization.

## 7.6. Definition of Baseline Value

Baseline is defined as the data point collected the closest, but prior to, the date and time when the first study transfusion is administered. In cases where the date is the same and the times are unknown, assessments taken on the same day are considered baseline.

## 7.7. Calculation of Study Day and Treatment Period

The day the subject receives their first post-randomization PLT transfusion will be considered Day 0. If the subject's PLT transfusion episode spans two calendar days, the day the transfusion started will be considered Day 0.

The treatment period is defined as the period of time from Day 0 through Day 27 or to the day of transfusion independence, defined as the last of ten (10) successive days after the last PLT transfusion (on- or off-protocol), whichever occurs first. Bleeding assessments are conducted at baseline and are to be conducted every day from Day 0 until the post-transfusion follow-up visit or early termination visit.

## 7.8. Definition of Visit or Windows

Visit labels, as collected in the database, will be used and no visit windows will be calculated.

## 7.9. Display of Treatment Groups

Unless specified otherwise, data will be summarized by study arm (MIRASOL vs CONTROL).

Treatment groups (arms) will be displayed as follows with respect to labels and ordering. Total columns may be provided for baseline assessments.

Groups	Definition
MIRASOL	Mirasol PLTs (MIR PLTs): LR-Trima Accel ® Aph-pathogen reduced (PR)-plasma PLT
CONTROL	Reference PLTs (REF PLTs): LR-Aph-plasma PLT

## 7.10. Subject Demographics and Baseline Characteristics

Subject demographics including date of birth, age (years) at informed consent, age group (Age <18, Age 18-65, Age > 65), sex, ethnicity (Hispanic and non-Hispanic), race (American Indian or Alaska Native, Asian, Black or African American, Native Hawaiian or Other Pacific Islander, White, Other, and Multiple), height, weight, and body surface area (BSA) will be listed by subject and summarized. Childbearing potential/pregnancy information for females will be listed. Age will be calculated as a continuous variable, where, the calculated value will be used in creating the different age groups. All demographic and baseline characteristics will be listed, and summaries will be generated using the mITT set and the SS. Summary tables will be presented by treatment group.

## 7.11. Concomitant Medication, Medical History and other Baseline Data

Concomitant medications will be listed and summarized.

Diagnosis and treatment including treatment type strata of allogeneic transplant, autologous transplant, and chemotherapy will be listed and summarized.

Medical and surgical history and history of transfusions will be listed by subject.

Blood type (ABO), ABO incompatibility and Rhesus factor (Rh) will be listed by subject.

## 7.12. Protocol Deviations

Subjects who are randomized into the study but who do not meet all major inclusion/exclusion criteria will be considered as having major protocol deviations. All protocol deviations reported by hospital study sites will be summarized by deviation type (major/minor) for the FAS population. All protocol deviations reported by hospital study sites including non-compliant transfusions and protocol deviations reported by blood centers will be listed for all screened subjects. Protocol deviations due to the COVID-19 pandemic can be identified through the standard text of 'Due to COVID-19' in the text of the deviation. A Blinded Data Review Committee (BDRC) will be formed and will review and classify possible protocol deviations for all subjects in the FAS as major or minor in a blinded fashion according to the BDRC Charter.

International Standard for the Transfer of Information Associated with Tissue Transplantation, Cellular Therapy and Blood Transfusion (ISBT) codes and corresponding definitions provided by the sponsor will be used in a read only manner to identify whether or not a platelet product meets the criteria either for the CONTROL group or the MIRASOL group transfusion per the CIP

Non-Compliant Transfusions are platelet transfusions that do not meet the platelet product requirements of the CIP. For subjects randomized to MIR treatment, ISBT codes categorized as anything other than 'MIRASOL' or 'Control Allowed' meet this criterion. For subjects randomized to Reference (REF), ISBT codes categorized as anything other than 'Control Allowed' meet this criterion. Non-compliant transfusions are protocol deviations, but they cannot be reported as protocol deviations in the database because that would potentially unblind users of the database. Instead, non-compliant transfusions are identified through ISBT codes and will be summarized and listed as separate protocol deviations.

## 7.13. Treatment Exposure

Exposure to platelet transfusions will be conducted on the mITT set and the SS by reason for transfusion.

One or multiple study platelet transfusions can occur anytime from Study Day 0 to Study Day 27 per subject. If a subject received a platelet unit within four (4) hours of completion of transfusion of the preceding platelet unit, these transfusions will be considered part of a single platelet transfusion episode in analyses.

Additional blood products transfused will be analyzed based on the SS. The number of blood products transfused (other than PTLs), type of blood product transfused, and for RBC transfusions, whether the RBCs were leukocyte-reduced, will be summarized.

## 7.14. On- Off-Protocol Transfusions

On- and Off-Protocol Transfusion definitions are as follows:

Off-Protocol Transfusion: any kind of PLT transfusion, other than those to which the subject was randomized (MIR PLTs or REF PLTs), regardless of the reason for the transfusion. For subjects

randomized to MIR treatment (MIRASOL), ISBT codes defined by the sponsor as 'Control Allowed' or 'Control NOT Allowed' meet this criterion. For subjects randomized to CONTROL, ISBT codes defined by the sponsor as 'MIRASOL' or 'MIRASOL Not Used' meet this criterion.

On-Protocol Transfusion: non-MIR or MIR treated platelet product transfused according to randomization assignment. For subjects randomized to MIR treatment (MIRASOL), ISBT codes defined by the sponsor as 'MIRASOL' or 'MIRASOL Not Used' meet this criterion. For subjects randomized to CONTROL, ISBT codes defined by the sponsor as 'Control Allowed' or 'Control NOT Allowed' meet this criterion.

On- and off-protocol platelet transfusions will be reported on the SS and summarized by treatment group and reason for transfusion, i.e. prophylactic, therapeutic (bleeding event), and other. The total number of platelet transfusions and the number of transfusions on- and off-protocol will be reported. The mean, median, minimum and maximum number of transfusions per subject will be reported. The number and percent of subjects with at least 1 on-protocol transfusion will be reported along with the median, minimum, and maximum duration of the transfusion period in days. The number and percent of subjects who had at least 75% of transfusions on-protocol (part of the PPS definition) will also be reported.

Each subject's transfusion will be listed along with on- or off-protocol and non-compliance status described in Section 7.12.

## 7.15. Subject Disposition

Subject disposition will be listed and summarized. The number of subjects screened, number of subjects in the FAS, mITT set, PPS and SS, the subject's final study status, and the number of subjects terminating the study early with reasons for early termination will be summarized for all subjects.

Subjects with Inclusion/Exclusion criteria deviations will be listed by subject.

## 8. Efficacy Analysis

A single primary efficacy endpoint will be considered and investigated using a NI design. The primary efficacy endpoint is defined as the number of days on which bleeding was assessed and WHO grade 2 or higher bleeding was evident over the treatment period. The maximum number of days with bleeding assessments will be twenty-eight (28) as this is the duration of the treatment period. Bleeding events are defined using criteria according to the WHO Grading Scale for Bleeding. Appendix I contains the WHO Grading Scale for Bleeding annotated with the study's Bleeding Assessment (MIPLATE Annotated eCRFs) variable identifiers (Bx) and answers that correspond to the bleeding status. Subgroup analyses involving the primary efficacy endpoint will also be conducted.

### 8.1. Primary Endpoint

Bleeding assessments based on the WHO Grading Scale for Bleeding will be conducted at baseline to assess eligibility prior to randomization, as well as daily starting on Day 0 and continuing to the post-transfusion bleeding assessment OR until transfusion independence (the last day of ten [10] consecutive days without a PLT transfusion). Each bleeding assessment will document the WHO Bleeding Scale components observed over the course of the prior calendar day, from 00:00 to 23:59. As such, the analysis of the Primary Endpoint, and Secondary Endpoint #2, will be based on bleeding assessments collected on Day 1 thru Day 28 which represent bleeds which occurred on Days 0-27.

The total number of days with WHO grade 2 or higher bleeding is obtained by counting the total number of calendar days (00:00 to 23:59) on which bleeding was assessed and found to be present. For example, if a subject has WHO grade 2 bleeding on Day 1, grade 2 bleeding on Day 2, and grade 3 bleeding on Day 3, this is considered 3 days of grade 2 or higher bleeding. Hematomas (bruises), petechiae, and purpura

[figure not shown]
(e.g., types of bleeding that occur under the skin) represent unique cases in which they are only counted as additional days of bleeding if they are new or manifest in another anatomical location.

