### **6.1. Study Design**

This is a prospective, multi-center, controlled, randomized study in which a non-inferiority (NI) design will be employed to evaluate the clinical effectiveness of Mirasol (MIR)-treated versus Conventional (CONTROL) apheresis (Aph) platelets (PLTs) in subjects with hematologic malignancies with hypoproliferative thrombocytopenia expected to have PLT count(s)  $\leq 10,000/\mu\text{L}$  and requiring  $\geq 2$  PLT transfusions. Subjects will be randomized by a ratio of 1:1 (MIRASOL vs CONTROL group) using a permuted-block schedule stratified by investigational site and type of treatment (allogeneic transplant vs autologous transplant vs chemotherapy). Randomization will occur as close to the initiation of the first study transfusion as possible, within five (5) days prior to the anticipated initiation of PLT transfusion(s).

Subject participation will be for up to eighty-one 81 days; a 14-day screening period, a 28-day treatment period, and a 28-day follow-up period. Study Day (also referred to in this document as ‘Day’) 0 of the treatment period is defined as the day of the first study transfusion following randomization. The primary, secondary, and exploratory endpoints will be based on data captured during the treatment period (Day 0 to transfusion independence or Day 28, whichever comes first). Transfusion independence is defined as ten (10) days without a PLT transfusion prior to date of last contact or Day 28 whichever is earlier. The date of transfusion independence will be the 10th day without a PLT transfusion.

Daily bleeding assessments assess bleeding for the previous day. The first bleeding assessment to be used for analysis of primary and secondary endpoints etc., will be collected on Study Day 1 which assesses bleeding at Study Day 0. Bleeding assessments are planned to occur on Study Days 0-27 and at the post transfusion follow-up visit. Consequently, there will be a maximum of 28 bleeding assessment days used for analysis. The bleeding assessments to be included in analysis are greyed out the in schematic below.

Study Day	0 (first transfusion day)*	1	2	3	4	5	6	27	Post transfusion/ Follow-up (in some cases Study Day 28)
Day bleeding assessed (24 hours previous to Study Day)	-1	0	1	2	3	4	5	26	27 + 2-day window allowed for visit

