#### 1. Proportion of subjects with $\geq$ grade 2 bleeding.

For each study arm, the proportion of subjects with at least 1 day of grade 2 or higher bleeding Day 0 through Day 27 (or until transfusion independence is achieved) will be calculated, where,  $p_t$  denotes the proportion of the MIRASOL group and  $p_c$  denotes the proportion for the CONTROL group.  $p_t$  and  $p_c$  will be calculated using the equations below:

$$p_T = \frac{\text{Number of Subjects with } \geq \text{ grade 2 Bleeding (Test Arm per mITT)}}{\text{Total Number of Subjects in the Test Arm per mITT}}$$

$$p_C = \frac{\text{Number of Subjects with } \geq \text{ grade 2 Bleeding (Control Arm per mITT)}}{\text{Total Number of Subjects in the Control Arm per mITT}}$$

The difference between the MIRASOL and CONTROL arms ( $p_T - p_C$ ) will be reported along with the 95% CI about this difference. The 95% CI and the corresponding p-value will be generated using Fisher's exact test to test the superiority null hypothesis of  $p/p_c=1$ . Negative values of the reported difference favor the MIRASOL group.

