#### 2. Time to first grade 2 or higher bleed

The time to first grade 2 or higher bleeding will be analyzed using a log rank test comparing survival curves stratified by treatment group. The timeframe under consideration is defined from the day of the subject's first post randomization PLT transfusion to the day the subject experiences their first grade 2 or higher bleed. Subjects that do not experience a grade 2 or higher bleed will be censored at Day 27 or at date of transfusion independence (10th day without a PLT transfusion prior last follow-up day or Day 27 whichever is earlier), where appropriate. Subjects that do not complete the study or are lost to follow-up will be censored on the date of their last study visit in the treatment period. A Kaplan-Meier (KM) plot contrasting the two study arms will also be generated to provide a visual representation of probability of remaining free of a WHO grade 2 or higher bleed as a function of time since first post-randomization transfusion.

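### Day 0 bleeding is counted from midnight, so bleeding before the first study transfusion is scored as an outcome; this modestly dilutes the non-inferiority ratios, and no planned analysis shows by how much

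*SAP*

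**What the plan says.** All references are to the SAP; the document supplied as the protocol carries the same text, and the Clinical Investigation Plan (CIP) is not among the documents.

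- **Start of the clock.** Section 7.7: "The day the subject receives their first post-randomization PLT transfusion will be considered Day 0".
- **Scoring unit.** Section 8.1 scores bleeding by whole calendar day: "Each bleeding assessment will document the WHO Bleeding Scale components observed over the course of the prior calendar day, from 00:00 to 23:59".
- **Days counted.** Section 6.1 says the first assessment analysed "will be collected on Study Day 1 which assesses bleeding at Study Day 0". Section 8.1 uses the Day 1 to Day 28 assessments, "which represent bleeds which occurred on Days 0-27".
- **Secondary endpoints (8.2.2).** Endpoint 1 is "the proportion of subjects with at least 1 day of grade 2 or higher bleeding Day 0 through Day 27". Endpoint 2 runs from the day of the "first post randomization PLT transfusion to the day the subject experiences their first grade 2 or higher bleed". Endpoint 3 repeats endpoint 1 for grade 3 or higher.
- **Reason for transfusion.** Section 7.14 has transfusions "summarized by treatment group and reason for transfusion, i.e. prophylactic, therapeutic (bleeding event), and other", so the plan allows for a transfusion given because of a bleed.
- **Day -1.** The schematic in Section 6.1 shows an assessment on Study Day 0 covering Day -1. It falls outside the analysed set. It is not a term in the primary model (treatment only, 8.1.3), the imputation model (8.1.2), the supporting analyses (8.1.4) or the subgroup list (8.1.5).

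No rule separates Day 0 bleeding before the transfusion from Day 0 bleeding after it.

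**The concern.** Bleeding that precedes the first study platelets cannot be caused or prevented by them. Randomization makes it equally likely in both arms, so it adds about the same amount to each. When the true ratio is above 1, adding equal amounts to numerator and denominator moves the observed ratio toward 1. In a superiority test that costs power. In a non-inferiority test it makes a product at the margin look better than it is.

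The count endpoint is exposed by at most one directly observed day in 28 per subject. The ever-bled endpoint is more exposed, because one pre-treatment bleed settles the subject's outcome.

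The counting rule also sits awkwardly with the rest of the SAP. Section 7.6 defines baseline by the date and time of the first study transfusion. Section 8.4.4 identifies treatment-emergent events by comparing event and transfusion start times. Section 8.1.1 goes as far as simulating data so that bleeding under the wrong product is not attributed to the randomized arm.

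**Working it through.** **The plan's own figure.** Section 6.3.3 gives about 85% power with 558 mITT subjects (279 per arm), a true ratio of 1.1, margin 1.6 and one-sided 0.025. It gives neither the CONTROL bleeding rate nor the dispersion, so 85% cannot be reproduced independently. It can only be inverted for the standard error it implies:

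SE = (ln 1.6 - ln 1.1) / (1.960 + 1.036) = 0.3747 / 2.996 = 0.125.

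This SE is used below and is only as good as the stated power.

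**Primary endpoint.** Assume 1.5 counted bleeding days per CONTROL subject, of which b are before transfusion on Day 0. The true ratio applies to the rest, and b is equal in both arms. With a true ratio of 1.60:

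observed ratio = [b + (1.5 - b) × 1.6] / 1.5; one-sided error = Φ(ln(1.6 / observed) / 0.125 - 1.96).

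| b (days) | Share of CONTROL bleeding days | Observed ratio | One-sided error |
|---|---|---|---|
| 0.05 | 3.3% | 2.37 / 1.5 = 1.58 | 0.031 |
| 0.10 | 6.7% | 2.34 / 1.5 = 1.56 | 0.039 |

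Writing f for the share, observed = 1.6 - 0.6f. At f = 1/28, where Day 0 contributes only its calendar share and all of it is pre-transfusion, the ratio is 1.579 and the error 0.032. At f = 10% they are 1.54 and 0.049; at f = 20%, 1.48 and 0.091. Nothing in the documents points to the last two.

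**Secondary endpoint 1, margin 1.2.** Assume 50% of CONTROL subjects are counted as ever bleeding and a share d of each arm bleeds before transfusion on Day 0. With a true ratio of 1.20 for the rest:

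observed ratio = [d + (0.50 - d) × 1.2] / 0.50.

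Section 8.1.3 does not fix the test statistic for this ratio margin, so the error below assumes a Wald test on the log risk ratio with 279 per arm.

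| d | Observed risk ratio | One-sided error |
|---|---|---|
| 2% | 0.596 / 0.50 = 1.19 | 0.030 |
| 5% | 0.590 / 0.50 = 1.18 | 0.041 |
| 10% | 0.580 / 0.50 = 1.16 | 0.063 |

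A slightly different set-up, with post-transfusion CONTROL risk of 30% to 70% and pre-transfusion bleeds added independently, gives errors of 0.041 to 0.044 at 5% and 0.064 to 0.076 at 10%.

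**Effect of starting at Day 1.** A negative binomial simulation (279 per arm, 1,500 runs, true ratio 1.6, assumed 2.5 CONTROL bleeding days and dispersion 1.9) let 0%, 10% or 20% of subjects bleed before transfusion on Day 0. With Day 0 counted, the error was 0.027, 0.032 and 0.058. With Day 0 left out, it was 0.032, 0.025 and 0.024. Simulation noise is about √(0.025 × 0.975 / 1,500) = 0.004. The simulated pre-treatment bleeds end on Day 0.

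**Power for Days 1-27.** Take SE² = (1/μ_C + 1/μ_T + 2φ)/279. With μ_C = 2.5, the stated power implies φ = 1.80. Replacing μ_C by 2.5 × 27/28 = 2.41 gives SE = 0.1255 and power 84.8%, against 85.0%.

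**The case against.** Much can be said for the plan, and most of it stands.

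- **Calendar-day scoring is a workable convention, and the primary effect is small.** True. On the assumed values, 1.60 moves to 1.58 or 1.56. If most first transfusions are prophylactic, it moves less.
- **Eligibility may keep out bleeding subjects.** The criteria are in the CIP, so this cannot be checked. Section 6.1 asks for randomization as close to the first transfusion as possible. It also allows up to five days before the anticipated transfusion, so a pre-randomization assessment cannot exclude bleeding that starts on Day 0.
- **The 1.6 margin may rest on data counted in the same way.** Its justification is also in the CIP. If so, the dilution is partly built into the margin.
- **An off-protocol first transfusion removes the day.** If all platelets on Day 0 are off-protocol, the primary analysis replaces that day by simulation. Conversely, an on-protocol Day 0 bleed feeds the individual rate used to simulate later off-protocol days. If off-protocol use differs by arm, that component need not pull toward 1.
- **Day -1 status might count as baseline.** Section 7.6 would admit a Day 0 assessment made before the transfusion. The gap is narrower: no named model or sensitivity analysis uses it.

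A reader might infer three stronger things that the documents do not support. First, that a subject bleeding on Day -1 is thereby an event or can have no later first bleed: Day -1 is not scored, and such a subject can have a first counted bleed on any later day. Second, that endpoint 2 is biased toward non-inferiority: it is a log-rank comparison without a margin, so dilution only hides a difference. Third, that a formal claim on endpoint 1 is at risk: Section 7.4 treats secondary outcomes as supportive and exploratory, and the main test in 8.2.2 is a superiority Fisher test.

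**Conclusion.** The point holds as a modest weakness that is cheap to address. Grade 2 or higher bleeding before the first study transfusion on Day 0 counts as an outcome. Its direct effect is anti-conservative for the one formal non-inferiority test and for the supportive margin of 1.2 on endpoint 1. For endpoint 2, and for endpoint 3, which has no stated margin, it only dilutes a difference.

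The size cannot be determined from the documents. On the assumed inputs, the primary one-sided error at the margin rises from 0.025 to about 0.03 to 0.04. For endpoint 1 it rises to about 0.03 to 0.06 at 50% CONTROL risk. These figures assume equal pre-treatment bleeding in both arms and, for the primary endpoint, the standard error implied by the stated power. They do not show that the primary conclusion would be unsound. They show that the plan has no analysis that would reveal whether Day 0 matters.

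**What to change.** Keep the mITT set and the Days 0-27 definition for the main analyses, and add two items to the SAP.

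1. **Baseline covariate.** Add Day -1 grade 2 or higher bleeding status (yes/no, from the Study Day 0 assessment) to the negative binomial model, at least as a prespecified adjusted analysis. State the rule for a missing assessment, and say that status is defined by the day covered even if the form is completed after the transfusion. This addresses prognosis and chance imbalance; it does not remove pre-transfusion Day 0 bleeding.
2. **Days 1-27 sensitivity analysis.** Repeat the primary analysis (offset up to ln 27) and secondary endpoints 1 to 3 counting from Day 1, with the margins of 1.6 and 1.2 where they apply. For endpoint 2, start time at Day 1 and keep subjects who bled on Day 0 in the risk set. Report how many subjects have no assessed day after Day 0, since they cannot contribute.

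Do not exclude subjects because of Day 0 bleeding or the recorded reason for transfusion. That would select on post-randomization data that may include bleeding after the transfusion, and it would depart from the mITT set that Section 8.2.2 requires.

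The cost is SAP wording and a few extra tables from data already collected. The sensitivity analysis omits true post-transfusion bleeding on Day 0 and does not remove pre-treatment bleeds that persist into Day 1, so it should be read beside the main analysis and not in place of it.
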